## 2 Objective

The objective of this study is to establish a large multicenter prospective cohort of patients with VRE BSIs to provide solid observational data that will aid in the design of randomized clinical trials on therapeutics and diagnostics for deep-seated VRE infections. To this end, clinical and epidemiological data will be collected on patients who have VRE isolated from the bloodstream during hospitalization, as well as descriptions of the outcomes of patients treated with various antimicrobial regimens. VRE isolates will also be collected to perform molecular and genomic characterization.

## **2.1 Aim 1. To assemble a multicenter prospective cohort of patients with VRE BSIs to provide data on outcomes of patients with VRE BSIs for sample size calculations for future trials**

We will leverage from an ongoing effort (VENOUS I) that has prospectively collected data from ca. 200 patients with enterococcal infections from three active centers to assemble a large multicenter cohort of patients with VRE BSIs. The data collected under this protocol will provide valuable information regarding outcomes and prognostic factors (both from the patient and isolate perspective), along with real-life data on which patients are the target population for any trial directed against invasive VRE infections. Also, we expect this cohort to help pinpoint specific geographic areas and/or centers with high incidence of VRE infections, facilitating the rational selection of sites for future trials. Data on outcomes (i.e. survival and microbiologic clearance) will aid in guiding the design of future clinical trials by providing reliable information needed for power and sample size calculations (see 3.3 in main MDRO protocol).

## **2.2 Aim 2. To provide data on the impact of potential inclusion/exclusion criteria on enrollment in future VRE trials**

Detailed clinical data will be collected to guide the future development of clinical trials. The eCRF is designed to collect data on the most common barriers to enrollment in clinical trials. Data can then be used in the design of future trials to be presented to pharmaceutical companies, as well as to regulators from the FDA. The information will also be used to provide a rationale for requesting exceptions in inclusion/exclusion criteria. This valuable data will result in the design of clinical trials that are more readily generalizable (see 3.2 in main MDRO protocol).

## **3 Exploratory Aim. To collect VRE isolates causing BSIs in order to understand the molecular epidemiology of infecting organisms for future studies**

All infecting VRE isolates will be collected for further microbiological, molecular and genomic characterization, as part of future studies. Bacterial genomic information will be analyzed in order to find possible genetic factors that correlate with clinical outcomes in deep-seated VRE infections.

## **4 Enrollment Target**

200 unique admissions. This will be a competitive enrollment.

## **5 Study Population**

All patients admitted to one of the participating hospitals who develop a confirmed blood stream infection due to VRE will be included in the study. In order to enroll a patient, the VRE isolate should be available for further characterization.

## **6 Clinical Definitions**

**VRE BSI:** At least one blood culture positive for vancomycin-resistant enterococci (resistance to vancomycin will be defined by current CLSI guidelines), regardless of the Enterococcal species and of the susceptibility method used by the microbiology

laboratory.

## Appendix IV:

POP: Prospective Observational *Pseudomonas* study

### List of Abbreviations

POP	Prospective Observational Pseudomonas study
CRPA	carbapenem-resistant P. aeruginosa
BSI	Blood Stream Infection

## 1 Background

*Pseudomonas aeruginosa* infections are common in immunocompromised patients, are a leading cause of hospital-acquired infection, and are associated with poor outcomes. Treatment of *P. aeruginosa* infections is complicated by antimicrobial resistance, including resistance to carbapenems. Carbapenem resistance is especially challenging because it is often associated with resistance to multiple classes of antibiotics, leaving few therapeutic options. Novel technologies and drugs are needed to better diagnose and treat *P. aeruginosa* infections, but designing the clinical trials necessary to address this demand is challenging given the lack of detailed data on *P. aeruginosa* resistance mechanisms, clinical and molecular epidemiology, treatment, and outcomes. This proposal aims to fill this gap by providing detailed clinical and microbiologic data in carbapenem-resistant *P. aeruginosa* (CRPA) pulmonary and bloodstream infections. We believe that this study is ideal for the ARLG, as it will utilize the existing the MDRO Network, which already has similar ongoing studies in patients with carbapenem-resistant Enterobacteriaceae and carbapenem-resistant *Acinetobacter* infections.

## 2 Objectives

### 2.1 Aim 1

Define antibiotic resistance determinants and molecular epidemiology of CRPA pulmonary and bloodstream infections within the ARLG MDRO network.

### 2.2 Aim 2

Facilitate future interventional and diagnostic studies involving CRPA by detailing current epidemiology, treatment, and outcomes of CRPA pulmonary and bloodstream infections at potential clinical trial sites within the ARLG MDRO Network.

### 3 Enrollment Target

The study will enroll up to 2000 unique admissions. This will be a global competitive enrollment.

### 4 Study population

#### 4.1 Inclusion criteria

All patients at participating sites, including pediatric patients, with CRPA isolated from any clinical culture during hospitalization or within 3 days prior to hospitalization will be included in the study.

#### 4.2 Exclusion criteria

1. Outpatient status at the time of collection of cultures that yield CRPA and patient not admitted to the hospital for CRPA infection within 3 days of collection of the culture
2. Cystic fibrosis

### 5 Clinical Definitions

**CRPA:** *Pseudomonas aeruginosa* isolates that are resistant in vitro to at least one of the following carbapenems: doripenem, imipenem, meropenem.

### 6 Statistical Analysis Plan

#### 6.1 Sample Size Estimate

The sample size will be approximately 2000 unique admissions.

## 1 Introduction

### 1.1 Purpose

This Statistical Analysis Plan (SAP) describes the planned and ad hoc analyses for Study Network of *Acinetobacter baumannii* as Carbapenem-Resistant Pathogen (SNAP), part of the Multi-Drug Resistant Organism Network (MDRO), an observational study of Carbapenem-Resistant *Acinetobacter baumannii* (CRAB). This SAP outlines the general statistical approaches that will be used in the analysis of the study. It has been developed to facilitate discussion of the statistical analysis components among the study team, and to provide agreement between the study team and statisticians regarding the statistical analyses to be performed and presented in the statistical analysis report. Post hoc discussions are included in this plan.

Analyses for the Primary Analysis Report will be initiated once the CRF database has been frozen for analysis, central lab antibiotic susceptibility testing (C-AST) results have been received, and whole genome sequencing (WGS) results have been received.

### 1.2 Key updates to SAP

Version	Changes Made	Rationale	Effective Date
1.0	Original Version		

## 2 Protocol Overview

### 2.1 Study Design

This study is specifically designed to provide data which can help in the design of future randomized clinical trials on both therapeutics and diagnostics, and describe, on the basis of observational data, patients with CRAB infections in hospitalized patients. These data will include a detailed clinical and epidemiological description of patients including potential barriers to enrollment in future trials. In addition, data will be collected on species, strain type, and mechanism of drug resistance of the causative organism.

A cohort will be constructed for CRAB eligible patients by investigating hospitalized patients who have CRAB isolated in clinical cultures from any anatomical site. This study will be conducted under a waiver of informed consent to facilitate universal inclusion. All patients who are admitted to one of the participating hospitals and who have CRAB – as defined in the specific sub-study protocol (Appendix) – isolated in a clinical culture are targeted for inclusion.

### 2.2 *A priori* and *Post Hoc* Analyses

The following comparisons were defined *a priori*:

- Geographic region
- Geographic region, limited to infections
- Infection vs colonization (non-infection)
- Presence of a carbapenemase
- Presence of a carbapenemase, limited to infections
- Modeling

- DOOR probability
- Inverse probability weighted (IPW) DOOR probability

The following comparisons were *post-hoc*:

- Central Meropenem MIC levels
- Central Meropenem MIC levels, limited to infections
- Clonal Group 2 vs other clonal groups
- Clonal Group 2 vs other clonal groups, limited to infections
- Modeling
  - Logistic regression model with site as random effect

### 2.3 Hypotheses

CRAB infection is associated with significant morbidity and mortality, including in comparison with CRAB colonization (non-infection). Specific patient characteristics and clinical outcomes, and molecular and microbiological of the strains, will differ across regions, information which will aid in the design of randomized clinical trials on therapeutics and diagnostics for CRAB infections.

### 2.4 Study Objectives

The objective of this study is to provide observational data that will aid in the design of randomized clinical trials on therapeutics and diagnostics for CRAB infections. To this end, clinical and epidemiological data will be collected on patients who have CRAB isolated from clinically indicated cultures during hospitalization as well as descriptions of the outcomes of patients treated with various antimicrobial regimens. Molecular and microbiological characterization will also be performed on CRAB isolates.

#### 2.4.1 Primary Objectives

- To determine 30 day all-cause mortality of CRAB infections

#### 2.4.2 Secondary Objectives

- To determine 30-day Desirability of outcome Ranking (DOOR) of CRAB infections
- To determine 90-day all-cause mortality of CRAB infections
- To elucidate antimicrobial susceptibility and molecular epidemiology of the index CRAB strains

### 2.5 Inclusion criteria

Inclusion criteria for the MDRO protocol was all hospitalized patients, including pediatric patients, who have at least one MDRO (CRAB for this analysis) isolated from a clinical culture will be eligible for inclusion.

Additional inclusion criteria for this analysis:

- Meets study carbapenem resistance requirement (resistant to at least one carbapenem, other than ertapenem, per susceptibility testing at the local lab)
- Outcome information available for 30 days post index culture

Subjects will be excluded from the analysis for the following reasons:

- WGS sequencing result not useable
- WGS did not detect acinetobacter baumannii
- C-AST not resistant to meropenem

### 3 Statistical Methods

#### 3.1 General considerations

- Global tests of statistically significant differences across any of the regions are provided. For pairwise comparisons between regions, USA will be the reference group.
- Tables are summarized by region, infection/colonization, meropenem MIC levels, presence of carbapenemase, and Clonal Group 2 vs other clonal groups.
- Categorical variables are tested using the chi-square test. Continuous variables and ordered categorical variables are compared using the Kruskal Wallis test.
- The Miettinen-Nurminen (score) method is used to calculate the confidence interval (CI) of the difference in proportions.
  - Please note that the only censoring is administrative censoring at 30 days. As this is an observational study with information collected from the medical record, unless subjects are known to have died, they are considered to be alive.
- Modeling will be limited to subjects with an infection.
- DOOR probabilities are calculated using Halperin CI.
- IPW adjustment for DOOR probability and difference in proportions will be utilized.
- Logistic regression is performed with study site as random effect.
- Analyses will be summarized for all subjects and repeated for the subset of subjects with an infection.
- Throughout this report we consider  $p < 0.05$  with a two-sided test to be statistically significant.

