## 5.2 Outcome analyses

The difference in proportion in 30- and 90 day mortality will be summarized with confidence intervals. The IPW difference in proportion, with 95% CI, will also be summarized. Pairwise DOOR probabilities and 95% CI will be estimated using Halperin's method. Both an unadjusted and IPW adjusted DOOR probability with 95% CI will be estimated. IPW models for infection vs. non-infection comparisons included:

- Geographic region
- Immunocompromising conditions
- Preadmission location (home origin vs other)
- Age-adjusted Charlson comorbidity index

IPW models for regional comparisons (infections only) included:

- Anatomical source of infection
- Immunocompromising conditions
- Preadmission location (home origin vs other)
- Age-adjusted Charlson comorbidity index

Post hoc, a logistic regression model was used to explore risk factors for mortality. Variables included in the analysis were:

- Geographic region (USA as reference)
- Anatomical source of infection (blood as reference)
- Aged-adjusted Charlson comorbidity index
- Immunocompromising conditions
- Pre-admission location
- Monomicrobial vs polymicrobial culture
- Acquired carbapenemase gene
- Clonal group (CG2 as reference)
- Capsular polysaccharide locus (KL)
- Lipooligosaccharide outer core locus (OCL)
- Site (random effect)

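### Regional comparisons of mortality and DOOR use methods that assume independent admissions, although region is fixed within site; for the IPW versions clustering is not addressed

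*SAP*

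**What the plan says.** SAP 2.2 lists geographic region, in all subjects and in infections only, among the a priori comparisons. SAP 3.1 sets out the testing: "Global tests of statistically significant differences across any of the regions are provided. For pairwise comparisons between regions, USA will be the reference group". The threshold is two-sided p < 0.05.

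The methods for the unadjusted comparisons are:

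- Tests: "Categorical variables are tested using the chi-square test. Continuous variables and ordered categorical variables are compared using the Kruskal Wallis test".
- Mortality differences: "The Miettinen-Nurminen (score) method is used to calculate the confidence interval (CI) of the difference in proportions".
- DOOR, in SAP 5.2: "Pairwise DOOR probabilities and 95% CI will be estimated using" Halperin's method. SAP 3.1 also names Halperin for DOOR probabilities in general.

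For the weighted analyses SAP 5.2 says: "The IPW difference in proportion, with 95% CI, will also be summarized". An IPW-adjusted DOOR probability with a 95% CI is promised as well. The list introduced by "IPW models for regional comparisons (infections only) included" holds anatomical source, immunocompromising conditions, preadmission location and age-adjusted Charlson index. It has no site term.

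Site enters one analysis, listed in SAP 2.2 as post hoc: "Logistic regression model with site as random effect". It is a mortality model that includes "Geographic region (USA as reference") as a covariate, together with carbapenemase gene, clonal group, KL and OCL.

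**The concern.** Sites are hospitals at fixed locations, and SAP 5 reports enrollment by region and by site within region. I infer that every admission at a site carries the same region. A regional contrast is then wholly a between-site contrast, and any variation between sites within a region goes straight into it. Chi-square, Kruskal-Wallis, Miettinen-Nurminen and Halperin, in standard form, count admissions as independent and leave that variation out of the standard error.

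If sites differ, a regional difference in 30-day mortality, 90-day mortality or DOOR will be called significant too often. Its interval will also look more precise than it is to those designing the next trial, which is the use SAP 2.3 gives for regional differences.

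**Working it through.** **Inputs from the documents.** Two-sided level 0.05 (SAP 3.1). Target of about 2000 admissions (Protocol Appendix II, 7.1). Background 30-day mortality of 16% to 58% (Protocol Appendix II, 1).

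**Inputs assumed.** ICC, number and size of sites, number of regions, and the DOOR distribution; also a 25% death rate where stated. For scale, 2000/50 = 40, 2000/100 = 20 and 2000/200 = 10 admissions per site, before any exclusion.

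**The plan's own figure.** With ICC = 0, the level is 2 × (1 − Φ(1.96)) = 0.050. Simulated chi-square and Kruskal-Wallis tests at ICC 0 rejected in 4.4% to 5.6% of runs. The nominal level is therefore right when sites do not differ.

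**With clustering.** For m admissions per site, the design effect is DE = 1 + (m − 1) × ICC, and a correct CI is √DE times as wide. The true pairwise level is 2 × (1 − Φ(1.96/√DE)). For a global test of four assumed regions it is P(χ²₃ > 7.81/DE).

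| m | ICC | DE | CI factor | Pairwise level | Global level, 4 regions |
|---|---|---|---|---|---|
| 10 | 0.01 | 1.09 | 1.04 | 6.0% | 6.7% |
| 20 | 0.02 | 1.38 | 1.17 | 9.5% | 12.9% |
| 20 | 0.05 | 1.95 | 1.40 | 16.0% | 26.1% |
| 40 | 0.10 | 4.90 | 2.21 | 37.6% | 66.1% |

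**Does the death rate matter?** Beta-binomial simulation of the chi-square test (10 vs 10 sites, 20 per site) at mortality 16%, 37% and 58% gave 10.2%, 9.7% and 10.3% at ICC 0.02, and 16.6%, 15.8% and 15.7% at ICC 0.05. The pairwise result hardly changes over the protocol's range.

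**Unequal site sizes.** At ICC 0.05, with 25% mortality, 15 vs 15 sites and a mean of 20 per site, a coefficient of variation of 0.8 in site size raises the pairwise mortality level to 20.7%.

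**DOOR.** Assume category shares of 30/25/20/25% with death at 25%, 15 vs 15 sites, 20 per site, and a site effect on a latent normal scale sized to give the stated ICC for death. The independent-row test then rejects in 12.5% of runs at ICC 0.02 and 21.0% at 0.05.

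**IPW.** For the risk difference the SAP names no variance method. For IPW DOOR, Halperin may be intended, but in standard form it handles neither weights nor clusters. If a row-level sandwich variance were used, simulation in the same setting at ICC 0.05 gives 15.6% for the risk difference and 18.9% for DOOR. Those two figures are conditional on a choice that the SAP does not state.

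**The case against.** **The SAP already has a site random effect.** It does, and it yields one site-adjusted regional odds ratio for mortality, so a reader should not conclude that site is ignored throughout. But that model is post hoc, conditions on strain characteristics and so answers a different question, and gives no risk difference and nothing for DOOR.

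**The target may be only the participating hospitals.** Independent-row variance would then be defensible. Protocol Appendix II, 2.1 gives this some support, since it uses the data to find high-incidence centers and choose sites. SAP 2.3, however, uses regional differences in patients, outcomes and strains to inform future trials, which reaches beyond the enrolled hospitals. The site random effect points the same way.

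**The size is entirely assumed.** This stands. The first row of the table is close to harmless. SAP 2.5 removes subjects and the IPW regional models use infections only, so clusters there will be smaller than 2000 implies and the lower values are more likely. The 38% and 66% figures need 40 per site and an ICC of 0.10; they are not estimates for this study.

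**The IPW intervals are wrong.** A reader might infer this, but the documents do not support it. They leave clustering unaddressed, which is not the same as showing that an independent-row variance was used.

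**Conclusion.** The point holds for regional comparisons of 30-day mortality, 90-day mortality and DOOR. If sites within a region differ at all, the unadjusted p-values are too small and the CIs too narrow. For the IPW versions the SAP does not say how clustering is handled. The direction is sure for any positive ICC; the size is not. Over the assumed range the pairwise mortality level runs from 6% to 38%, with 9.5% to 16% at 20 admissions per site and ICC 0.02 to 0.05, and no inflation at ICC 0. The one inference about the design is that region is constant within site.

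It would be tempting to extend this to every p-value in the report, or to the mortality result itself. The documents do not support that here. Region is in neither the primary nor the secondary objectives (SAP 2.4.1 and 2.4.2), and infection vs colonization can vary within a site, so the argument above does not carry over. Nor does the point show that any regional difference is false. It should be fixed, but it limits regional statements only.

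**What to change.** In SAP 3.1 and 5.2, for regional comparisons of mortality and DOOR only:

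1. Keep the point estimates, but base CIs and p-values on a variance clustered by site with a small-sample correction. A site jackknife or site bootstrap within region would do for the unadjusted and IPW versions alike, re-estimating the weights in each replicate.
2. State that this is the IPW variance method, for both the risk difference and DOOR.
3. Report sites and admissions per region beside the results.
4. Where a region has too few sites for this, or if the change is not made, label its p-values and CIs as descriptive of the participating sites.
5. Label the change as post hoc, since SAP 4 dates the data freeze and transfers to 2020 through 2022.

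No new data are needed: site is recorded and enrollment by region/site is already a report component. Programming is moderate. The real price is wider regional CIs and lower power, which is marked when a region has few sites. For illustration, assume 20 vs 6 sites, 20 admissions each, ICC 0.02 and mortality of 25% vs 40%. With a site-level variance, power is about 73% with a normal reference (which is not exact with so few sites), 60% with Satterthwaite degrees of freedom, and 52% with degrees of freedom from the smaller region. The choice of correction therefore matters and should be written down.

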#### 3.2 Outcome measure definitions

**Carbapenem susceptibility:** a culture is included if it has a corresponding susceptibility form with documented resistance at the local lab to at least one carbapenem (meropenem, imipenem, doripenem).

**Infection vs. colonization (non-infection):** only cultures that meet the study surveillance definition of infected are counted as infected. For CRAB, respiratory isolates are considered to be infected if the respiratory diagnosis on the CRF was tracheobronchitis, pneumonia, no mechanical ventilation, ventilator-associated pneumonia, or an “other” diagnosis identified by 2 study investigators ([name] and [name]). All other cultures, including cultures missing information needed for the assignment of infection/colonization (non-infection), are considered to be colonized (not infected).

**30-day mortality:** an admission is considered alive at 30 days if they are not recorded as dead. If an admission is discharged alive and there is no other information on the 90-day form or if they have a discharge date but no disposition, then they are assumed to be alive.

**90-day mortality:** an admission is considered alive at 90 days if they are not recorded as dead. If an admission is discharged alive and there is no other information on the 90-day form or if they have a discharge date but no disposition, then they are assumed to be alive.

**DOOR:** The DOOR variable reported in MDRO studies is an ordered categorical variable measuring status at 30 days following the culture collection date. The categories are:

- Clinical Response at 30 days, with no events
  - Symptomatic response, no anti-CRAB antibiotic, no relapse
- 1 event
- 2 or 3 events
- Death

The possible events are:

- No clinical response at 30 days
- “Bad” discharge within 30 days or readmitted within 30 days
- Renal failure post-culture or *C. difficile* infection.

